1.3. Schedule of Activities (SoA)

Table 1 Time and Events Table

Procedure	Pre- Screen	Screenin g	Treatment Period (visit window is ± 7days)			IP Discontinu ation visit	End of study visit	Notes			
Visit		1	2	3	4	5	6	7		8	
Week		-2 to -1	0	4	8	12	16	20	4 weeks post last dose ± 7 days	24 or Early Withd rawal	
Written Informed Consent	X	X									 Pre-screen visit can occur on the same day as the Visit 1 but must be completed prior to starting Visit 1 (screening) procedures. Visit 2 (Week 0) must occur at least one week following Visit 1 (screening) Visit 2 (Week 0) will be considered Baseline
Demography		X								:	
Medical History		X									
Asthma and Exacerbation History (including triggers)		Х									
Asthma Therapy History		X									Therapy history to include a detailed review of prior monoclonal antibodies received for treatment of asthma, including prior investigational anti-IL5 or anti-IL13 preparations.

Procedure	Pre- Screen	Screenin g		Treatment Period (visit window is ± 7days)			IP Discontinu ation visit	End of study visit	Notes		
Visit		1	2	3	4	5	6	7		8	
Week		-2 to -1	0	4	8	12	16	20	4 weeks post last dose ± 7 days	24 or Early Withd rawal	
Oral Corticosteroid Therapy History		X									
Smoking History		X									
Cardiovascular History/risk factors		X									
Parasitic Screening		X									
Inclusion/Exclusion Criteria		х	х								Study inclusion/exclusion criteria should be reviewed at the beginning of visit 2(Week 0). The review should include the results of any lab/safety assessments conducted at Visit 1 (screening).
Treatment Period Criteria			x								
Efficacy Assessments						_		_			
Exacerbation review			х	X	X	х	х	х	X	Х	Number of clinically significant exacerbations (including exacerbations requiring hospitalization, Emergency Department) visits will be evaluated
Spirometry including FEV ₁ , FVC		Х	х		Х		Х		X	Х	

Procedure	Pre- Screen	Screenin g	Treatment l		7days)				IP Discontinu	End of study	Notes
									ation visit	visit	
Visit		1	2	3	4	5	6	7		8	
Week		-2 to -1	0	4	8	12	16	20	4 weeks post last dose ± 7 days	24 or Early Withd rawal	
Maximum Post Bronchodilator Procedure		х	x						х	X	Maximum Post Bronchodilator Procedure is required to complete reversibility testing. If participant does not reverse ≥12% in FEV₁ at Visit 1 (screening), the procedure may be repeated at Visit 2 (Week 0).
OCS dose adjustment review (where applicable)		Х		х	Х	Х	Х	Х			OCS dose adjustment should be reviewed at scheduled in-clinic Visits

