For safety reasons alerts will be programmed into the eDiary to encourage the participant to contact the investigator if their asthma worsens (see Appendix 9). However, an alert in itself will not be classified as a clinically significant exacerbation.

8.1.3. Pulmonary Function Testing including Reversibility using the Maximum Post-Bronchodilator Method

Spirometry will be conducted, using the Spirometry equipment provided by GSK through a designated central laboratory at the visits specified in the Time and Events schedule. The spirometer should meet American Thoracic Society standards and produce a printout of all data generated, which should be stored in the participant's notes. The spirometer should be calibrated in accordance with the manufacturer's instructions and a calibration log maintained. Participants should withhold short-acting beta-2-agonists (SABAs) for ≥ 6 hours and LABAs for ≥ 12 hours prior to clinic visit. Assessments to be recorded will include FEV₁, and FVC.

Pre-bronchodilator measurements will be taken at baseline, week 8, 16, and 24. In addition, at visit specified in the Time and Events schedule, post-bronchodilator values will be recorded following reversibility testing, using the maximum post bronchodilator method. For participants unable to achieve ≥12% reversibility and 200mL change at Visit 1 (screening), reversibility can be repeated at Visit 2 (Week 0). The procedures to achieve the maximum post-bronchodilator are those generated by the Asthma Clinical Research Network. Further details of spirometry and reversibility testing procedures are presented in the SRM.

8.1.4. eDiary

The participant will be asked to record the following parameters daily in the eDiary from Visit 1 (screening) onwards:

- Morning peak flow (best of three), before rescue medication usage (L/min)
- Number of puffs of rescue usage over the previous 24-hours
- Asthma symptom score over the previous 24-hours using a 6-point scale (Appendix 8)
- Frequency of awakening due to asthma symptoms requiring rescue medication use.
 - Daily dose of OCS

The participant will be asked to complete the ACQ-5 weekly in the eDiary from Visit 1 (screening) onwards.

From Visit 1 (screening) to Visit 2 (Week 0) only, participants will record peak flow twice a day to allow for calculation of PEF diurnal variability.

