	• Analysis of change from baseline in clinic pre-bronchodilator FEV ₁ and post-bronchodilator FEV ₁ at Week 24 will be performed analysed as separate endpoints using a mixed models repeated measures (MMRM) analyses, allowing for covariates of visit, baseline maintenance OCS use (yes, no) and exacerbations in the year prior to the study (as an ordinal variable). All data will be included in the endpoint analysis will be from the start of treatment until the week 24 visit, regardless of treatment discontinuation. Mean change from baseline in FEV ₁ will be summarised and presented with 95% confidence interval by visit. Comparisons will be Week 24 vs. Baseline, and all data collected up to and including Week 24, including participants who have discontinued study treatment, will be included in the analyses. Missing data (following early withdrawal) will be assumed to be missing at random (MAR) following subject withdrawal from the study.
	• Analysis of change from baseline in ACQ-5 score will be performed using a mixed models repeated measures (MMRM) analysis, allowing for covariates of visit, baseline maintenance OCS use (yes, no) and exacerbations in the year prior to the study (as an ordinal variable). All data will be included in the endpoint analysis will be from the start of treatment until the week 24 visit, regardless of treatment discontinuation. Mean change from baseline in ACQ-5 score will be summarised and presented with 95% confidence interval by visit. Comparisons will be Week 24 vs. Baseline, and all data collected up to and including Week 24, including participants who have discontinued study treatment, will be included in the analyses. Missing data (following early withdrawal) will be assumed to be missing at random (MAR) following subject withdrawal from the study.
	• Analysis of change from baseline in morning PEF during Weeks 20 –

Endpoint	Statistical Analysis Methods

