7.2.8. Common Calculations

Each subject's age will be calculated based on their date of birth relative to the date of the screening visit. Where only a subject's year of birth is collected, their date of birth will be imputed with 30th June (30 Jun YYYY).

Body Mass Index (kg/m^2) = Weight $(kg)/Height (m)^2$.

The predicted normal FEV1 and reversibility values are recoded in the CRF as per the protocol assessment visits. The predicted normal FEV1 is based on the NHANES III equations as described in the protocol and Asian equation will be used for Asian race.

Reversible is defined as an increase in FEV1 of ≥12% and ≥200mL following administration of bronchodilator (albuterol/salbutamol) at any protocol assessment visit.

Non-reversible is defined as a post-bronchodilator (post-albuterol/salbutamol) increase in FEV1 of <200mL or increase that is <12% from pre-bronchodilator (pre-albuterol/salbutamol) FEV1.

A subject is considered achieved asthma control between Week 20 and Week 24 if he/she does not have a clinically significant exacerbation during this period between W20 and W24. The process for assessing clinically significant exacerbations of asthma is provided in Appendix9. Visit Windows.

Where a subject does not prematurely withdraw from the study, or the subject withdraws prematurely from the study at a scheduled visit, there are no plans to derive visit windows; visits will be used in the analyses as reported on the CRF.

For subjects prematurely withdrawing from the study, the EOS, unscheduled or IP discontinuation visit will initially be remapped to the next scheduled protocol specific assessment visit for each parameter, if the visit falls ±7 days of next scheduled planned visit (see below). Otherwise, the data will be remapped to the next planned scheduled visit. If there are more than one assessment associated with a particular visit interval, then the visit will be remapped to that with the closest target day. If subject having multiple records on same day for parameter (lab, ECG etc), then for continuous parameter data average value and for categorical parameter data, worst value will be presented. Please reframe the text accordingly.

| Visit | Target Day | Window (Days) |
|-------------------|------------|---------------|
| Visit 3 (Week 4) | 28 | 21 to 35 |
| Visit 4 (Week 8) | 56 | 49 to 63 |
| Visit 5 (Week 12) | 84 | 77 to 91 |
| Visit 6 (Week 16) | 112 | 105 to 119 |
| Visit 7 (Week 20) | 140 | 133 to 147 |

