10.2.2. Forced Expiratory Volume in 1 second (FEV1)

Analysis of change from baseline in clinic pre-bronchodilator FEV1 at Week 8, Week 16 and Week 24 will be performed using a mixed models repeated measures (MMRM) analysis, including visit and asthma exacerbations in the year prior to the study (as an ordinal variable -0, 1, 2, 3+) and baseline maintenance OCS use (yes, no) (binary nominal variable) as an as covariates. Change from baseline in pre-bronchodilator FEV1 value along with a two-sided 95% confidence interval and p-value estimated from MMRM model will be presented. The following SAS code will be used:

proc mixed data=modeldata; class usubjid avisitn; model chg = avisitn BASEOCSD PEXACCTN / solution ddfm=kr cl htype=**3**; Ismeans avisitn / cl pdiff e; repeated avisitn / subject= usubjid type=un; run;

Where, chg = change from baseline in clinic pre-bronchodilator FEV1 at Week 8, Week 16 and Week

Avisitn = Visit BASEOCSD = baseline maintenance OCS use (Yes/No) PEXACCTN = asthma exacerbations in the year prior to the study

An unstructured covariance structure will be used in the model. If there are any convergence issue, then an alternative compound symmetric, autoregressive (AR(1)), Toeplitz covariance structure will be used.

Treatment policy strategy will be used for treatment discontinuation (for any reason). This will estimate the treatment effect at the end of the 24 week study period regardless of treatment discontinuation.

Treatment policy strategy: The occurrence of the intercurrent event is considered irrelevant in defining the treatment effect of interest: the value for the variable of interest is used regardless of whether or not the intercurrent event occurs.

A similar analysis will be conducted for the post-bronchodilator FEV1 value at Week 24. In addition, descriptive summaries for the actual and change from baseline values for pre- and post-bronchodilator FEV1 will be presented by scheduled visits.

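### Post-bronchodilator FEV1 has one common post-baseline visit, so its planned MMRM is a single-visit regression that ignores earlier lung function and leaves early exit values unclear

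*SAP*

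**What the plan says.** Protocol 9.4.2 treats the two FEV1 endpoints together. The change from baseline "at Week 24 will be performed analysed as separate endpoints using a mixed models repeated measures (MMRM) analyses", with visit, baseline maintenance OCS use and prior-year exacerbations as covariates, and with all data to Week 24 included regardless of treatment discontinuation. It adds: "Missing data (following early withdrawal) will be assumed to be missing at random (MAR) following subject withdrawal from the study".

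SAP 10.2.2 gives code for pre-bronchodilator FEV1, with an unstructured covariance and the statement "model chg = avisitn BASEOCSD PEXACCTN / solution ddfm=kr cl". Baseline FEV1 is not a term. For the other endpoint it says: "A similar analysis will be conducted for the post-bronchodilator FEV1 value at Week 24". It does not repeat the missing-at-random sentence or replace it, and SAP 10.7 imputes nothing for FEV1.

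The measurement schedules differ. Protocol 8.1.3 says "Pre-bronchodilator measurements will be taken at baseline, week 8, 16, and 24", whereas "at visit specified in the Time and Events schedule, post-bronchodilator values will be recorded following reversibility testing". In the Schedule of Activities (protocol 1.3) the post-bronchodilator row is marked at Visit 1, Visit 2, the IP discontinuation visit and Visit 8 (Week 24 or Early Withdrawal), and at no visit from Week 4 to Week 20.

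For participants who leave early, the visit-window text under SAP 7.2.8 says that "the EOS, unscheduled or IP discontinuation visit will initially be remapped to the next scheduled protocol specific assessment visit for each parameter" when it falls within 7 days of the next planned visit. Otherwise the data move to the next planned visit.

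**The concern.** An MMRM is useful under missing at random because a participant's earlier outcomes inform the missing final one. That works for pre-bronchodilator FEV1, which has values at Weeks 8 and 16. Post-bronchodilator FEV1 has nothing comparable, so the same label covers a different and weaker analysis.

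If people with a poor interim response withdraw more often, the Week 24 mean rests on the better responders. There is no control arm in which the same selection might partly cancel. The lung-function data that would reveal the selection are collected but not used for this endpoint.

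**Working it through.** **1. Plan figures.** The documents state no SD, effect, correlation or dropout rate for FEV1, so there is no plan figure to reproduce for this endpoint. The one input taken from them is 100 treated participants (protocol 9.2; 100/0.65 = 153.8, which matches the stated 154 screened).

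**2. Count the visits.** Common post-baseline visits: pre-bronchodilator 3 (Weeks 8, 16, 24), post-bronchodilator 1 (Week 24). Protocol 1.3 puts baseline at Visit 2 and SAP 7.2.2 puts it at Visit 1; the count is the same either way.

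**3. Reduce the model.** An unstructured matrix over *t* visits has *t*(*t*+1)/2 parameters: 3×4/2 = 6 for pre-bronchodilator, 1×2/2 = 1 for post-bronchodilator. With one value per participant the visit term is constant, V = σ²I, and REML equals ordinary least squares on participants with a value. In a numerical check, 71 of 100 simulated participants had a value. The REML and OLS residual variances were both 0.16025, and the other 29 contributed nothing.

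**4. What remains of missing at random.** If missingness depends only on a covariate in the model, and the fitted mean is averaged over all treated participants, simulated bias is 0.001 SD. Conditioning on interim or baseline FEV1 is lost.

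**5. Size when withdrawal follows interim response.** Assumptions:
- SD of change 0.30 L.
- Correlation ρ of 0.6–0.8 between Week 24 post-bronchodilator change and Week 16 pre-bronchodilator change.
- P(withdraw) = expit(a − bZ), with Z the standardised Week 16 change, b = 0.5 or 1, and a set to give the withdrawal rate.
- No exit values.

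Then bias = ρ × SD × E(Z | stays), and SE ≈ 0.30/√(number remaining). E(Z | stays) is found by numerical integration.

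| Withdrawal | E(Z given stays), b = 0.5 / 1 | Lowest: 300 mL × 0.6 × E | Highest: 300 mL × 0.8 × E | SE |
|---|---|---|---|---|
| 5% | 0.0247 / 0.0471 | 4.4 mL | 11.3 mL | 300/√95 = 30.8 mL |
| 10% | 0.0488 / 0.0908 | 8.8 mL | 21.8 mL | 300/√90 = 31.6 mL |
| 20% | 0.0962 / 0.1732 | 17.3 mL | 41.6 mL | 300/√80 = 33.5 mL |

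Simulating the same set-up gives 5–11, 9–22 and 17–41 mL, which agrees within about 1 mL.

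**6. Does borrowing repair it?** In simulations with 100 participants, slope 1 per SD and correlations of 0.5 and 0.7, the single-visit bias was 0.03 SD at 5% withdrawal, 0.05–0.06 at 10%, 0.09–0.12 at 20% and 0.13–0.17 at 30%. Conditioning on the Week 8 and 16 values left at most 0.006 SD (0.006 × 300 = 2 mL).

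**7. Baseline FEV1.** If low baseline FEV1 drives withdrawal, and change correlates −0.3 with baseline (assumed), the bias reverses. It is −0.02 to −0.08 SD over 5–30% withdrawal (−6 to −24 mL at 0.30 L). Interim visits alone left −0.01 to −0.05 SD; a baseline covariate brought it within 0.003 SD.

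**8. Exit values.** Suppose an exit value moves to the next visit at which this parameter is scheduled. That visit is Week 24, so the value is in effect carried forward. Suppose instead it moves to the next planned visit of any kind. It then sits on a visit level held only by withdrawers, with no within-person link to Week 24. Neither reading lets earlier lung function inform a missing Week 24 value.

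**The case against.** A reader might infer that this is a pure complete-case analysis in which everyone without a Week 24 visit is discarded. The documents do not support that. The post-bronchodilator procedure is also due at the Early Withdrawal and IP discontinuation visits, protocol 7.2 asks for an end-of-study visit if possible, and SAP 7.2.8 provides for remapping. Only withdrawers with no exit spirometry are certain to drop out.

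A reader might also infer that missing at random is abandoned or concealed. It is an assumption, stated openly in protocol 9.4.2, and the regression is valid under it when missingness depends only on the two covariates. The protocol calls the FEV1 endpoints separate and promises no borrowing between them. What stands is narrower: the model cannot condition on earlier lung function.

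The practical stakes are also limited. Protocol 7.2 expects withdrawal to be uncommon and asks that participants who stop drug stay in the study. Appendix 10 allows home spirometry under COVID-19 restrictions. This is one of seven secondary endpoints in a study with no formal hypothesis test. These points argue for a proportionate change. They do not remove the mismatch between the method named and the data scheduled.

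**Conclusion.** The concern holds in this limited form. The planned MMRM for post-bronchodilator FEV1 is a Week 24 regression on available values, it omits baseline FEV1, and the handling of exit values is ambiguous.

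The size is illustrative because every input except the 100 participants is assumed. When withdrawal follows interim response and no exit values exist, the overstatement is well below one standard error at 5–10% withdrawal. At 20% it is roughly half to one and a quarter standard errors (17.3/33.5 = 0.52; 41.6/33.5 = 1.24). If half the withdrawers gave exit values that matched their Week 24 values, it would be about half as large. If baseline FEV1 drove withdrawal, the sign could reverse. A reader might wish to express the bias as a percentage of the treatment effect, but the documents give no expected change, so no such percentage can be supported.

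**What to change.** Amend SAP 10.2.2 before database lock:

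- Analyse Week 24 post-bronchodilator change jointly with pre-bronchodilator change at Weeks 8, 16 and 24, with an unstructured covariance over the four outcomes (4×5/2 = 10 parameters). Alternatively, multiply impute Week 24 post-bronchodilator FEV1 from its baseline value and the pre-bronchodilator values.
- Include baseline FEV1 as a covariate.
- State in SAP 7.2 that early exit values are not counted as Week 24 in this analysis, and use them as auxiliary data at their actual time.
- Report the Week 24-only regression as a sensitivity analysis, labelled as available-case.
- State the missing-at-random assumption in the SAP, with the variables it conditions on.

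The cost is SAP wording and one extra model. The schedule already collects all the data required.

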10.2.4. Peak Expiratory Flow (PEF)

Analysis of change from baseline in morning PEF during each 4-weeks reporting period of Weeks 1-4, Weeks 5-8, Weeks 9-12, Weeks 13-16, Weeks 17-20 and Weeks 21-24 will be performed using a mixed models repeated measures (MMRM) analysis described in section 10.2.2, including reporting period and asthma exacerbations in the year prior to the study (as an ordinal variable – 0, 1, 2, 3+) and baseline maintenance OCS use (yes, no) (binary nominal variable) as covariates. Change from baseline in morning PEF along with two-sided 95% confidence intervals and p-values estimated from MMRM model will be presented.

All data will be included in the endpoint analysis will be from the start of treatment until the week 24 visit, regardless of treatment discontinuation.

Comparisons will be Weeks 20–24 vs. Baseline, and all data collected up to and including Weeks 20–24, including participants who have discontinued study treatment, will be included in the analyses. Missing data (following early withdrawal) will be assumed to be missing at random (MAR) following subject withdrawal from the study.

In addition, descriptive summaries for the actual and change from baseline values in morning PEF values will be presented by 4-weeks reporting period.

Treatment policy strategy will be used for treatment discontinuation (for any reason). This will estimate the treatment effect at the end of the 24 week study period regardless of treatment discontinuation.

Treatment policy strategy: The occurrence of the intercurrent event is considered irrelevant in defining the treatment effect of interest: the value for the variable of interest is used regardless of whether or not the intercurrent event occurs.

10.3. STATISTICAL METHODS FOR HEALTH OUTCOME ENDPOINTS

10.3.1. Clinician and Subject Rated Response to Therapy:

The clinician and subject rated overall evaluation of response to therapy at Week 8, Week 16 and Week 24 will be assessed using a 7-point scale: $1 = \frac{1}{2}$

Counts and percentage of subjects with each response category will be summarized separately for clinician and subject rated overall evaluation of response to therapy by scheduled visit.

Treatment policy strategy will be used for treatment discontinuation (for any reason). This will estimate the treatment effect at the end of the 24 week study period regardless of treatment discontinuation.

Treatment policy strategy: The occurrence of the intercurrent event is considered irrelevant in defining the treatment effect of interest: the value for the variable of interest is used regardless of whether or not the intercurrent event occurs.

10.3.2. Work Productivity and Activity Impairment Questionnaire: General Health (WPAI-GH)

The WPAI-GH is a self or interviewer administered tool comprised of 6 questions which address absenteeism, presenteeism (reduced effectiveness while working), overall work productivity loss (absenteeism plus presenteeism), and activity impairment based on the data from the past 7 days. The WPAI-GH responses are scored as impairment percentages, with a higher percentage indicating greater impairment and less productivity. The following WPAI-GH composite scores will be derived:

[figure not shown]
- Percent work time missed due to health: Q2/(Q2 + Q4)
- Percent impairment while working due to health: Q5/10
- Percent overall work impairment due to health: Q2/(Q2+Q4) +[(1-Q2/(Q2+Q4)) x (Q5/10)]
- Percent activity impairment due to health: Q6/10

The above WPAI-GH composite scores and change from baseline will be summarized by visit using number of subjects, mean, SD, median, minimum and maximum values.

Treatment policy strategy will be used for treatment discontinuation (for any reason). This will estimate the treatment effect at the end of the 24 week study period regardless of treatment discontinuation.

Treatment policy strategy: The occurrence of the intercurrent event is considered irrelevant in defining the treatment effect of interest: the value for the variable of interest is used regardless of whether or not the intercurrent event occurs.

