8.1.7. Work Productivity and Activity Impairment Questionnaire: General Health (WAPI-GH)

Asthma has a substantial effect on lost days of works, with millions of days being lost each year (Catley, 2011). Furthermore, asthma results in lost productivity due to decreased effectiveness while working (Wilson, 2012). The WPAI-GH is a self or interviewer administered tool comprised of 6 questions which address absenteeism, presenteeism (reduced effectiveness while working), overall work productivity loss (absenteeism plus presenteeism), and activity impairment. This validated tool captures data from the past 7 days. WPAI-GH outcomes are scored as impairment percentages, with a higher percentage indicating greater impairment and less productivity (Reily Associates, 2018).

Participants will initially complete the paper questionnaire, and then the study designated site staff will transcribe the information into the eCRF.

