10.1. EFFICACY ANALYSIS SRATEGY

10.1.1. SECONDARY EFFICACY ENDPOINTS

There are no primary efficacy endpoints defined for this study. The efficacy analysis is defined in terms of secondary and other efficacy endpoints as below:

10.1.2. Secondary Endpoints:

- Number of clinically significant exacerbations.
- Number of exacerbations requiring hospitalization or ED visits
- Number of exacerbations requiring hospitalization
- Change from baseline in clinic pre-bronchodilator FEV1 at week 24
- Change from baseline in clinic post-bronchodilator FEV1 at week 24
- Change from baseline in ACQ-5 score at week 24
- Change from baseline in morning PEF during weeks 20 24.

10.1.2. Health Outcome Endpoints:

- Clinician and Subject rated response to therapy at Week 24
- Mean change from baseline in WPAI-GH composite scores (percentage) at week 24:
 - Percent work time missed due to general health
 - Percent impairment while working due to general health
 - Percent overall work impairment due to general health
 - Percent activity impairment due to general health

10.1.3. Exploratory Endpoints:

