10.7. IMPUTATION OF MISSING DATA

Missing values will be treated as missing unless and otherwise specified. If a subject experience a clinically significant asthma exacerbation between Weeks 20-24, then for the purpose of assessing percentage of subjects achieving at least 50% reduction in OCS dose during the weeks 20-24, the subject will be imputed into the worst-case category of 'no reduction in OCS Dose'. For the analysis of median percent OCS reduction during weeks 20-24, the subject will be imputed using the maximum dose of OCS observed during the 4-Weekly period across all participating subjects.

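### The SAP's WPAI-GH formulas give 0-to-1 fractions under a percent label and, where Q5 is blank, lose an overall-impairment score already fixed at its maximum

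*SAP*

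**What the plan says.** SAP 10.3.2 states the scale: "The WPAI-GH responses are scored as impairment percentages, with a higher percentage indicating greater impairment and less productivity". Protocol 8.1.7 says the same, and the health outcome list in SAP 10.1 gives the endpoint as "Mean change from baseline in WPAI-GH composite scores (percentage) at week 24".

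SAP 10.3.2 then prints four formulas (final brackets are trimmed from the first and third quotes):

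- The absenteeism score is a ratio of two hour counts: "Percent work time missed due to health: Q2/(Q2 + Q4".
- The presenteeism score rescales a single item: "Percent impairment while working due to health: Q5/10".
- The overall work score combines the two above: "Percent overall work impairment due to health: Q2/(Q2+Q4) +[(1-Q2/(Q2+Q4)) x (Q5/10".
- The score for daily activities again rescales one item: "Percent activity impairment due to health: Q6/10".

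Neither document gives the wording, response range or skip pattern of Q1 to Q6. Neither has a rule for a blank Q5, for a week with no hours, or for participants who are not in work. The only general rule is in SAP 10.7: "Missing values will be treated as missing unless and otherwise specified". By contrast, SAP 10.2.3 does set a rule for unanswered ACQ-5 items.

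The planned output is a descriptive table by visit (SAP 10.3.2). Protocol 9.4.3 plans no statistical analysis of these scores.

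**The concern.** There are two separate faults.

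The first is scale. The text promises percentages and the formulas deliver fractions. A programmer who follows the formulas will fill a percent table with values between 0 and 1.

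The second is a case in which the formula already determines the answer but the written rules discard it. Someone who missed every work hour for health reasons has the highest possible overall impairment. The Q5 term then has weight zero, so Q5 is not needed. If Q5 is empty, a literal calculation still returns missing, and SAP 10.7 leaves it so. The loss is one-sided, because every score removed in this way is a maximum. At stake are the visit means of overall work impairment, and the mean change if such weeks are more frequent at one visit than at the other.

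**Working it through.** The documents state no numerical WPAI-GH result, so there is no plan figure to reproduce. The check evaluates the printed formulas.

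**Inputs.** The formulas come from SAP 10.3.2. From their labels, Q2 is read as hours missed for health and Q4 as hours worked. Q5 is taken as a 0-to-10 item. That range is an assumption, but the overall formula only makes sense if Q5/10 is on the same 0-to-1 scale as the absenteeism fraction. Write A = Q2/(Q2 + Q4) and overall = A + (1 − A) × Q5/10.

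**Scale.**

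| Q2, Q4, Q5 | A | Q5/10 | Overall |
|---|---|---|---|
| 8, 32, 5 | 0.20 | 0.50 | 0.20 + 0.80 × 0.50 = 0.60 |
| 20, 20, 8 | 0.50 | 0.80 | 0.50 + 0.50 × 0.80 = 0.90 |

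Multiplied by 100, the first row becomes 20%, 50% and 60%.

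**No hours worked.**

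| Q2, Q4, Q5 | A | Overall |
|---|---|---|
| 40, 0, 0 | 1 | 1 + 0 × 0 = 1 |
| 40, 0, 10 | 1 | 1 + 0 × 1 = 1 |
| 40, 0, blank | 1 | 1 + 0 × missing = missing |
| 0, 0, blank | 0/0, undefined | undefined |

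In the third row the absenteeism score is kept at its maximum, and the activity score is kept if Q6 is answered. The score for impairment while working is also empty, but properly so, since there was no working time to rate. Only the overall score is lost although its value is known.

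**Effect on a visit mean (assumed inputs).** Let a share f of scored workers be lost in this way and let the others average m%. The mean is then too low by f × (100 − m) points.

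| f | m = 50 | m = 30 |
|---|---|---|
| 2% | 1.0 | 1.4 |
| 5% | 2.5 | 3.5 |
| 10% | 5.0 | 7.0 |

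**Effect on mean change (assumed inputs).** Let the others average 40% at baseline and 25% at Week 24, so that −15 points is reported. With shares s at baseline and t at Week 24, the full mean change is [100t + 25(1 − t)] − [100s + 40(1 − s)] = −15 − 60s + 75t.

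| s | t | Full change | Reported |
|---|---|---|---|
| 5% | 1% | −17.25 | −15 |
| 10% | 2% | −19.5 | −15 |
| 15% | 5% | −20.25 | −15 |
| 10% | 10% | −13.5 | −15 |

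Under these means the direction turns at s = 1.25t. Above that the reported improvement is too small, and below it too large. The −15 also assumes that 40% and 25% are the means among participants scored at both visits, because change is computed within participant.

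**The case against.** The strongest reply is that this is notation plus an unseen premise. The percent label tells any reader that 0.60 means 60%, and the ordering of participants does not change. A figure just above the formulas is not shown in the public text, so a scaling note there cannot be ruled out. Protocol 8.1.7 cites a published scoring source for the instrument, which may cover both scaling and special cases. Nothing in the documents shows that Q5 is left blank in a week without work.

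Much of this stands, and it limits the point. A reader might infer that the overall formula fails for anyone absent all week. It does not: with any answered Q5 it correctly returns the maximum, and a participant absent for non-health reasons is in the different 0/0 case. A reader might also infer that the most impaired participants drop out of the WPAI-GH analysis. They keep the absenteeism score and, if Q6 is answered, the activity score. The table also reports the number of subjects at each visit, so a loss would be partly visible.

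What does not stand is that nothing needs changing. The printed formulas and the stated scale disagree, and the SAP is the document the programmer follows. A cited source could settle the special cases only if the SAP adopted its rules, which SAP 10.3.2 does not do.

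**Conclusion.** The point holds in two limited parts. The printed formulas are off the declared scale by a factor of 100. That part needs no assumption about Q5 being blank, and it stands unless the figure not shown supplies the scaling. The second part is conditional: if Q5 is blank when Q2 > 0 and Q4 = 0, the rules as written turn a determined maximum into a missing value. A blank Q5 is plausible because the item rates impairment while working, but it remains an assumption.

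It would be tempting to conclude that improvement is understated. The documents do not support a direction or a size. They give neither the share of participants in work nor the frequency of fully missed weeks at either visit, and equal shares of 10% reverse the sign in the illustration above. The consequence is confined to a descriptive exploratory summary. No primary or secondary endpoint is affected, so this is a desirable correction and not an urgent one.

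**What to change.** In SAP 10.3.2:

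- Multiply all four scores by 100.
- If Q2 > 0 and Q4 = 0, set overall work impairment to 100%, whether or not Q5 is answered.
- If Q2 + Q4 = 0, or the participant is not in work, treat absenteeism and overall work impairment as not applicable, and count these separately from missing. Name the item or CRF field that records work status.

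The cost is a few lines of SAP text and the matching derivation code. No new data and no change to the protocol are needed.
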